6.3 Assignment to study intervention

Randomization numbers will be assigned at the site in an unblinded fashion and will be entered into ClinBase.

6.4 Blinding

This is an open-label study. Blinding will not be performed.

6.5 Study intervention compliance

For all study participants, minzasolmin will be administered at the study site.

When participants are dosed at the site, they will receive study intervention directly from the investigator or designee, under medical supervision. The date and time of each dose administered in the clinic will be recorded in the source documents. The dose of study intervention and study participant identification will be confirmed at the time of dosing by a member of the study site staff other than the person administering the study intervention.

6.6 Dose modification

There is no dose modification allowed in UP0152.

6.7 Continued access to study intervention after the end of the study

There will be no access to study intervention after the end of the study.

6.8 Treatment of overdose

For all study participants, minzasolmin will be administered at the study site. No treatment for overdose is recommended by UCB and treatment for overdose should be at the discretion of the principal investigator.

6.9 Concomitant medication(s)/treatment(s)

6.9.1 Permitted concomitant therapy (medications and therapies)

The following concomitant medications are permitted during the study:

- Paracetamol/acetaminophen for the treatment of mild symptoms (eg, headache or other pain), given at most every 6 hours to 8 hours, not exceeding 2g per day, and with a total of no more than 5g over 7 days
- Ibuprofen, not exceeding 1.2g per day
- Oral contraceptives not exceeding 30µg ethinyl estradiol or postmenopausal HRT or implants, patches, or IUDs/IUSs delivering progesterone (for female study participants)

6.9.2 Prohibited concomitant therapy (medications and therapies)

Concomitant medications are not allowed with the exceptions listed in Section 6.9.1.

6.9.3 Rescue medication

No rescue medication will be provided as part of this study.

[figure not shown]
7 DISCONTINUATION OF STUDY INTERVENTION AND PARTICIPANT DISCONTINUATION/WITHDRAWAL

7.1 Discontinuation of study intervention

7.1.1 Liver chemistry stopping criteria

Study intervention will be discontinued immediately and permanently for a participant if liver chemistry stopping criteria are met.

Figure 7-1: Phase 1 liver chemistry stopping algorithm

ALT=alanine aminotransferase; AST=aspartate aminotransferase; INR=international normalized ratio; ULN=upper limit of normal

Specific assessments and follow-up actions for potential drug-induced liver injury (PDILI) are provided in Appendix 6 (Section 10.6).

7.1.2 Corrected QT interval stopping criteria

A participant who meets either bulleted criterion based on single 12-lead ECG readings will be withdrawn from the study. If there are abnormalities that are considered clinically significant for a particular study participant, ECG recordings will be performed in triplicate at 2- to 3-minute intervals (3 ECGs within a 5-minute timeframe) before the exclusion of the participant.

- QTcF >500ms OR Uncorrected QT >600ms
- Change from Baseline (Day -1, before first treatment, Day 6, and Day 11) of QTcF >60ms

If a clinically significant finding is identified (including, but not limited to, changes from Baseline in QTcF after enrollment, the investigator or qualified designee will determine if the participant can continue on the study intervention and if any change in participant management is needed. This review of the ECG printed at the time of collection must be documented. Any new clinically significant finding should be reported as an AE.

See the Schedule of Activities (Section 1.3) for data to be collected at the time of intervention, discontinuation and follow up and for any further evaluations that need to be completed.

7.1.3 Temporary discontinuation

Study participants may be temporarily discontinued from study intervention (but not necessarily from the study) if there is a positive pregnancy test. Refer to Section 8.4.5 for additional procedures related to pregnancy in a study participant.

7.1.4 Hypersensitivity reaction stopping criteria

Study participants will be informed that if they develop any symptoms suggestive of a hypersensitivity reaction (eg, rash, angioedema, or anaphylaxis) they should contact the investigator immediately. The investigator should assess the presenting symptoms to determine if this is possibly a hypersensitivity reaction.

If the event is not considered to be a hypersensitivity reaction the investigator should document this, and the participant may continue dosing. If the event is possibly a hypersensitivity reaction, the investigator will withhold dosing and arrange additional investigations. Study participants may be referred to a dermatologist for additional investigation. The event should be reported to UCB as an AESI via the SAE reporting form.

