2.3 Benefit/risk assessment

This study will not provide a benefit to the study population, ie, healthy study participants. This study will provide relevant PK and clinical safety information to support minzasolmin new tablet formulation development.

A summary of possible risks and adverse reactions is provided in the IB based on a review of adverse event (AE) data from 98 study participants exposed to minzasolmin in completed clinical studies UP0030 (51 participants), TM0017 (4 participants), UP0077 (21 participants), and UP0078 (22 participants), and based on the review of safety data in the ongoing clinical studies UP0073 (42 participants), and PD0053 and its extension study PD0055 conducted in approximately 490 participants (from PD0053).

Overall, the majority of treatment-emergent adverse events (TEAEs) observed in clinical studies with minzasolmin to date were mild or moderate in intensity and resolved. In UP0030, 2 events of hypersensitivity were reported. An additional 2 events of hypersensitivity occurred in study participants who received minzasolmin in UP0077. A causal relationship between the reported events of hypersensitivity and minzasolmin is considered plausible. Hypersensitivity reactions are considered an important identified risk for minzasolmin and are further described in the IB.

There have been no reports of anaphylaxis in the minzasolmin clinical program.

Of all the adverse drug reactions reported in completed minzasolmin clinical studies, based on the frequency of occurrence, all are considered common ($\geq 1\%$ and $< 10\%$).

In the ongoing Phase 2 study (where participants are receiving daily doses of Study Drug for 18 months), of the 496 participants, 8 reports of aspartate aminotransferase (AST) and/or alanine transaminase (ALT) elevations > 3 times upper limit of normal (ULN) (of which 2 were > 10 times ULN)

have been received. In the majority of reports, the transaminase elevations were noted 2 to 3 months after the first dose of study medication. None of the reports had an increase in bilirubin or international normalized ratio (INR) and none met Hy's law criteria. Transaminase values decreased spontaneously without study drug discontinuation in 3 participants or after discontinuation of the drug in 5 participants.

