7.2 Participant discontinuation/withdrawal from the study

A participant may withdraw from the study at any time at the participant's own request for any reason (or without providing any reason).

A participant may withdraw at any time at the discretion of the investigator for safety, behavioral, compliance, or administrative reasons.

At the time of discontinuing from the study, if possible, an ETV should be conducted, as shown in the Schedule of Activities (Section 1.3). See Schedule of Activities for data to be collected at the time of study discontinuation and follow up and for any further evaluations that need to be completed.

The participant will permanently discontinue from the study intervention and the study at that time.

If the participant withdraws consent for disclosure of future information, the sponsor may retain and continue to use any data collected before such a withdrawal of consent.

If a participant withdraws from the study, the participant may request destruction of any samples taken and not tested, and the investigator must document this in the site study records.

See the Schedule of Activities (Section 1.3) for data to be collected at the time of study discontinuation and follow up and for any further evaluations that need to be completed.

Participants must be withdrawn from the study if any of the following events occur:

1. Participant develops a clinically relevant medical condition (physical or psychiatric) that, in the opinion of the investigator, jeopardizes or compromises the study participant's ability to participate in the study or makes it unsafe to continue.
2. Participant withdraws his/her consent.
3. The sponsor or a regulatory agency requests withdrawal of the participant.
4. Participant has a confirmed positive serum pregnancy test.

Participants should be withdrawn from the study if any of the following events occur:

1. Participant is noncompliant with the study procedures or medications in the opinion of the investigator.
2. Participant takes prohibited concomitant medications as defined in this protocol.

Investigators should attempt to obtain information on study participants in the case of withdrawal.

Investigators should contact the study physician, whenever possible, to discuss the withdrawal of a study participant in advance.

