8.4.6.1 Hypersensitivity reaction monitoring and management

If a study participant experiences a hypersensitivity reaction (such as rash, angioedema, or anaphylaxis), he or she will contact the clinical site immediately (24 hours a day) or seek urgent medical advice in accordance with instructions from the investigator.

The advice will be based on the clinical presentation and may be to present to the clinical site or seek medical attention in the community.

The study participant should be rapidly and thoroughly assessed in line with the actions below.

Hypersensitivity reactions will be AESIs and require expedited reporting to UCB, regardless of seriousness, expectedness, or relatedness in line with Section 8.4.6. This will allow for rapid evaluation.

Procedures for the management of minzasolmin are provided in Appendix 3 (Section 10.3).

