8.4.6.1.4 Treatment

Investigators will administer the appropriate treatment as deemed necessary in cases of hypersensitivity. This includes the use of antihistamines for urticaria and the appropriate management in case of potentially life-threatening events such as anaphylaxis, Stevens-Johnson Syndrome, and toxic epidermal necrolysis.

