8.4.6.1.6 Rapid referral to experts

Expert consulting (eg, dermatologist/allergist/immunologist) is required for expert opinion (diagnosis), diagnostic testing (eg, prick test for other potential allergens), further treatment, and follow up. Same day referral is required, especially if there is presentation of systemic symptoms or signs, or both.

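### The hypersensitivity rules conflict on referral and on treatment, and a pointer to a procedure that is not there leaves withheld dosing without a stated end

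*Protocol*

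**What the plan says.** Protocol Section 2.3 gives the risk its weight: "Hypersensitivity reactions are considered an important identified risk for minzasolmin and are further described in the IB". It also calls a causal link plausible.

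- **Dosing.** Section 7.1.4 is headed as stopping criteria and has two branches. If the investigator judges that the event is not hypersensitivity, dosing may go on. Otherwise: "If the event is possibly a hypersensitivity reaction, the investigator will withhold dosing and arrange additional investigations".
- **Referral.** Section 7.1.4 adds: "Study participants may be referred to a dermatologist for additional investigation". Section 8.4.6.1.3 lists rapid expert referral among the investigations that should be arranged. Section 8.4.6.1.6 requires an expert opinion and continues: "Same day referral is required, especially if there is presentation of systemic symptoms or signs, or both".
- **Treatment.** Section 8.4.6.1.4 has investigators give whatever treatment they deem necessary, and says "This includes the use of antihistamines for urticaria". Section 6.9.2 reads: "Concomitant medications are not allowed with the exceptions listed in Section 6.9.1". Section 6.9.1 lists paracetamol, ibuprofen, and hormonal contraception or replacement therapy. Among the events for which Section 7.2 says a participant should be withdrawn is: "Participant takes prohibited concomitant medications as defined in this protocol". Under Section 7.2, withdrawal ends both study intervention and study participation for good.
- **Management pointer.** Section 8.4.6.1 says: "Procedures for the management of minzasolmin are provided in Appendix 3 (Section 10.3".

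**The concern.** A site facing a possible reaction has to settle three things quickly: whether to refer, what may be given, and what happens to the doses still due on Days 6 and 11. On the first two, different sections give answers that cannot all be followed. On the third, the one section offered as the place to look does not contain the answer.

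The participant's handling is at stake first, for a risk that the protocol itself singles out. There are also consequences for the data:

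- The reading chosen can decide whether an event counts as a TEAE leading to withdrawal, which is a secondary endpoint. SAP Section 5.5.2 tabulates study discontinuation and permanent treatment discontinuation separately, so the distinction will show in the tables.
- SAP Section 5.1.1.2 makes prohibited concomitant medication a category of important protocol deviation. Deviations that affect the PK can remove data from the Pharmacokinetics Set (protocol Section 9.1.4, SAP Section 4).
- Dropouts are not replaced (protocol Section 9.4).

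**Working it through.** The plan gives no figure to reproduce here. The check is a comparison of texts, followed by a short calculation for context.

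**Step 1: is the trigger the same?** Section 7.1.4 acts when an event is possibly a hypersensitivity reaction. Section 8.4.6.1.2 describes the evaluation of a possible reaction, and Sections 8.4.6.1.3 to 8.4.6.1.6 belong to the same procedure. The two sets of rules therefore cover the same participant at the same moment.

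**Step 2: referral.**

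| Section | Strength | To whom |
|---|---|---|
| 7.1.4 | optional | dermatologist |
| 8.4.6.1.3 | should be arranged | dermatologist, allergist or immunologist |
| 8.4.6.1.6 | required, same day | expert, with the same three as examples |

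One action has three strengths. A site that reads only 7.1.4 and does not refer complies with 7.1.4 and breaches 8.4.6.1.6.

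**Step 3: treatment.** The chain is as follows.

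1. Section 8.4.6.1.4: an antihistamine is given for urticaria.
2. Section 6.9.1: antihistamines are not on the permitted list.
3. Section 6.9.2: anything off that list is not allowed, and no exemption is made for treating an adverse event. SAP Section 6.1.5 likewise limits continued medication to the protocol's list and allows no rescue medication.
4. Section 7.2: a participant who takes a prohibited medication should be withdrawn, and withdrawal is permanent.
5. Section 7.1.4: for the same participant, dosing is only withheld.

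Following the treatment section thus meets a withdrawal criterion, and no section says whether that is intended.

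**Step 4: end of withholding.** The liver rule (7.1.1) states an immediate and permanent stop. The QT rule (7.1.2) states withdrawal from the study for a participant who meets a criterion. Section 7.1.4 states neither a permanent stop nor a condition for closing the question. The pointer in 8.4.6.1 leads to Appendix 3, whose parts are the AE definition, the SAE definition, recording and follow-up (with intensity and causality), and SAE reporting. None concerns management of minzasolmin. Doses fall on Days 1, 6 and 11 with no stated window, so the text does not say what a withheld dose becomes.

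**Step 5: how often the rules might be used (context only).** Inputs from protocol Section 2.3: 2 events in UP0030 and 2 in UP0077, with 51 + 4 + 21 + 22 = 98 participants in the completed studies reviewed. The planned number is 18 (Section 9.4).

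- Rate: 4/98 = 4.08%.
- Expected among 18: 18 × 0.0408 = 0.73.
- Chance of at least one: 1 − (1 − 0.0408)^18 = 0.53.
- If the 4 events came from only 3 or 2 participants: 3/98 gives 0.43 and 2/98 gives 0.31.
- The exact 95% confidence interval for 4/98 is 1.1% to 10.1%. This gives 1 − (1 − 0.011)^18 = 0.18 up to 1 − (1 − 0.101)^18 = 0.85.

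All of this assumes that the earlier rate carries over to three single doses.

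**The case against.** The strongest reply is that the protocol can be applied sensibly as it stands.

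- **Dosing.** A reader might infer that a site may dose again after a possible reaction and still be in line with some section. The documents do not support this. Section 7.1.4 lets dosing go on only if the event is judged not to be hypersensitivity; otherwise it is withheld, and no other section lifts that. Section 7.2 also requires withdrawal when the investigator judges a medical condition makes it unsafe to continue, and allows the sponsor to request it. Section 8.4.6 has every such event reported within 24 hours. A route based on judgement therefore exists. This stands, and it makes the dosing point a gap. It does not supply the missing end state or repair the pointer. Section 7.1.3 names a positive pregnancy test as a ground for temporary discontinuation but does not say it is the only one, so nothing is built on it here.
- **Referral.** A site that follows the strictest text breaches nothing in 7.1.4, and a dermatologist is one of the experts named. That is true, but it requires the site to know that the later section governs, and 7.1.4 does not refer to it.
- **Treatment.** A specific instruction may be read as overriding a general bar, the withdrawal ground is a *should* and not a *must*, and withholding followed by withdrawal can be sequential. This softens the conflict. The protocol still states no such precedence, and literal compliance still meets the withdrawal ground.
- **Frequency.** A reader might take the 53% to mean that the rules will probably be needed. The documents do not establish that. Section 4.3 describes 21 and 28 days of dosing in UP0030 and UP0077. No hypersensitivity count is given for UP0073 (42 participants), whose design Section 4.2 calls similar. Exclusion criterion 7 removes people with an allergic predisposition. This objection stands in full.

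**Conclusion.** The protocol is inconsistent as written on referral and on the status of antihistamine treatment, and its pointer for managing minzasolmin leads to an appendix without that content. These findings rest on current text alone and hold whatever the event rate. The unstated end of withholding is a gap that the failed pointer makes worse. It is not a contradiction, and it does not amount to permission to dose again.

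The size cannot be given as a number. The chance that at least one of 18 participants needs these rules could be anywhere from about 18% to 85%, even assuming one event per participant and an unchanged rate, and three single doses may well carry less risk. Power is not the issue. The case for acting is that the rules concern a named important risk, they cannot all be followed, and correcting them is cheap. The change should be made, but it does not undermine the trial's main comparison.

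**What to change.** Reconcile protocol Sections 6.9.2, 7.1.4, 7.2, 8.4.6.1, 8.4.6.1.3 and 8.4.6.1.6 so that:

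1. Referral after a possible reaction is stated once, at one strength and with one timing, and the other sections refer to that statement.
2. Sections 6.9.2 and 7.2 say how medication given under 8.4.6.1.4 relates to the prohibited-medication withdrawal ground. The important-deviation criteria under SAP Section 5.1.1.2 should then follow the same reading.
3. The Appendix 3 pointer is replaced by a passage that gives the end state of withheld dosing: who closes the question, when, and what becomes of the remaining scheduled doses.

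What each rule should say is for the sponsor's physician; the requirement here is only that the sections agree. The cost is a wording amendment, with no added visits, tests or participants.

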7.1.5 Study stopping criteria

During the study, planned dosing and procedures must be discontinued or suspended for all remaining study participants who are yet to be dosed in the study and appropriate follow-up procedures established for (but not limited to) any of the following reasons:

- A pattern of AEs, considered as related to the study drug, occurs that in the opinion of the investigator and/or UCB Study Physician contraindicates the further dosing of additional study participants.
- If the sponsor or its designee judges it necessary for medical, safety, regulatory, or any other reasons consistent with applicable laws, regulations, and Good Clinical Practice (GCP).

Where it is possible to do so without threatening the safety of study participants, such discontinuation/suspension should be discussed with the UCB Study Physician before its implementation.

7.2 Participant discontinuation/withdrawal from the study

A participant may withdraw from the study at any time at the participant's own request for any reason (or without providing any reason).

A participant may withdraw at any time at the discretion of the investigator for safety, behavioral, compliance, or administrative reasons.

At the time of discontinuing from the study, if possible, an ETV should be conducted, as shown in the Schedule of Activities (Section 1.3). See Schedule of Activities for data to be collected at the time of study discontinuation and follow up and for any further evaluations that need to be completed.

The participant will permanently discontinue from the study intervention and the study at that time.

If the participant withdraws consent for disclosure of future information, the sponsor may retain and continue to use any data collected before such a withdrawal of consent.

If a participant withdraws from the study, the participant may request destruction of any samples taken and not tested, and the investigator must document this in the site study records.

See the Schedule of Activities (Section 1.3) for data to be collected at the time of study discontinuation and follow up and for any further evaluations that need to be completed.

Participants must be withdrawn from the study if any of the following events occur:

1. Participant develops a clinically relevant medical condition (physical or psychiatric) that, in the opinion of the investigator, jeopardizes or compromises the study participant's ability to participate in the study or makes it unsafe to continue.
2. Participant withdraws his/her consent.
3. The sponsor or a regulatory agency requests withdrawal of the participant.
4. Participant has a confirmed positive serum pregnancy test.

Participants should be withdrawn from the study if any of the following events occur:

1. Participant is noncompliant with the study procedures or medications in the opinion of the investigator.
2. Participant takes prohibited concomitant medications as defined in this protocol.

Investigators should attempt to obtain information on study participants in the case of withdrawal.

Investigators should contact the study physician, whenever possible, to discuss the withdrawal of a study participant in advance.

